Exclusion Criteria	
 • (1) Severe stenosis or occlusion of other arteries, or tandem stenosis proximal to the qualifying artery. • (2) Intracranial hemorrhagic diseases such as definite Intracranial tumors, any intracranial vascular malformations, hemorrhagic transformation of infarction, spontaneous intracranial hemorrhage (cerebral parenchymal, subarachnoid, subdural, or epidural) within 30 days. • (3) Non atherosclerotic intracranial arterial disease: arterial dissection, moyamoya disease or moyamoya syndrome demonstrated by imaging examination, or a definite medical history of autoimmune vasculitis. • (4) Evidence of cardioembolic embolism such as atrial fibrillation, prosthetic valve(s), infective endocarditis, mitral stenosis, atrial myxoma, intracardiac clot or vegetation, left ventricular aneurysms and so on. • (5) Known unstable angina or myocardial infarction within the last 6 months. • (6) Intolerance or allergic reaction to any treatment-related medication, including aspirin, clopidogrel, heparin, and local or general anesthetics. • (7) History of life-threatening allergy to contrast dye. • (8) Severe liver impairment (AST or ALT > 3 times normal, cirrhosis), serum creatinine > 3.0 mg/dl. • (9) Past history of EC-IC bypass surgery or EVT. • (10) Major surgery (including open femoral, aortic, or carotid surgery) within previous 30 days or planned in the next 90 days after enrollment. • (11) Late-stage malignant tumors, cachexia, or other serious diseases and an expected life expectancy of less than 1 year. • (12) Pregnant, perinatal stage or lactating women.
Treatments and Study Groups	
The technical feasibility of ER for all sNA-IAO patients in this study will be collaboratively evaluated by two experienced interventional neuroradiologists. The decision to select either medical treatment alone or additional ER is made by the patients themselves or their legal representatives. Patients are subsequently divided into two groups based on selection of treatment approach: the medical group and the ER group.

Follow-up schedule	Baseline, 30±7 days, 90±7 days, 1 year±30 days
Primary Outcome	
The primary outcome is a composite outcome as follows:
 
 • Any stroke or death within 30 days after enrollment • Ischemic stroke in the territory of the qualifying artery from 30 days to 1 year after enrollment.

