Secondary Endpoints	
Secondary outcomes as follows:
 
 • Mortality within 1 year; • Ischemic stroke outside the territory of the qualifying artery within 1 year; • Disabling stroke within 1 year; • TIA in the territory of the qualifying artery within 1 year; • Unplanned revascularization (EC-IC bypass surgery or ER) of the qualifying artery within 1 year; • Myocardial infarction within 1 year; • Composite vascular events within 1 year, including any stroke, myocardial infarction, and unplanned revascularization; • Quality of life assessment (EuroQol-5-Dimensions scale questionnaire) at 1 year; • mRS score at 1 year; • Periprocedural outcomes; • Restenosis or reocclusion (symptomatic or asymptomatic).
Statistical Methods	
 • Categorical variables will be compared between treatment groups using χ^2 or Fisher's exact test. Continuous variables or ordinal variables will be compared between treatment groups using t-test or Wilcoxon-Mann-Whitney test. • The primary and time-to-event secondary outcomes will be compared between the groups using log-rank test. • Kaplan-Meier curves will be used to show the incidence of outcomes over time. • The hazard ratio (HR) and adjusted hazard ratio (aHR) between groups, along with their 95% CIs, will be determined using univariate and multivariate Cox proportional hazards regression models. • Propensity score matching (PSM) will be performed to reduce the possible influence of selection bias and confounders on the outcomes. • A 2-sided P value less than 0.05 is considered to demonstrate a statistically significant difference. • All analyses will be performed with using SAS Version 9.4.

Schedule of assessments

Table 1: Summary of Study Treatment and Study Assessments

Study Requirements	Screening and Baseline	Endovascular recanalisation			Discharge	Follow-up Visits		
		Pre-procedure	Intra-procedure	Post-procedure		30-Day (±7 days)	90-Day (±7 days)	1-Year (±30 days)
Inclusion/Exclusion	X	X						
Informed Consent	X							
Clinical Assessment, Vital Signs, and Physical Exam	X	X			X	X	X	X
Laboratory tests	X					X	X	X
NIHSS (blinded to treatment)	X				X	X		
mRS (blinded to treatment)	X				X	X	X	X
EQ-5D (blinded to treatment)						X	X	X
mTICI assessment		X	X	X				
CT/MRI	X			X			X	X
CTP/PWI	X						X	X
CTA/DSA	X						X	X
Protocol Deviations		X	X	X	X	X	X	X
Medication review and patient compliance survey	X	X	X	X	X	X	X	X

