3.6 Treatments and Study Groups

The technical feasibility of endovascular recanalization for all sNA-IAO patients in this study will be collaboratively evaluated by two experienced interventional neuroradiologists. The decision to select either medical treatment alone or additional ER is made by the patients themselves or their legal representatives. Patients are subsequently divided into two groups according to the treatment they received: the medical group and the endovascular recanalization (ER) group. Patients in ER group will receive endovascular recanalisation procedure (details in procedure part below) plus medical treatment (same as the control group).

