3.6.1 Endovascular recanalisation (ER)

For patients presenting with ICA or MCA M1 segment occlusion, ipsilateral cerebral hemodynamic compromise is rigorously evaluated through computed tomography perfusion (CTP) or magnetic resonance perfusion imaging prior to enrollment according to a previous study.³¹ Moreover, the non-contrast and perfusion scans are additionally transferred to the Rapid Processing of Perfusion and Diffusion (RAPID) system, providing analysis of perfusion source images with respect to the DEFUSE 3 criteria¹³.

All patients who are scheduled to undergo ER should receive dual antiplatelet therapy (aspirin 100 mg per day and clopidogrel 75 mg per day) for at least three days before the procedure.

All procedures are performed under general anesthesia by an experienced interventional neuroradiologist. After placement of sheath introducers, heparin is given intravenously to maintain the coagulation time between 200 and 300 s. The 6- or 8- French guiding catheter is located distal to the occluded artery as much as possible. Under the route map, the micro guidewire in combination with a microcatheter and the microcatheter are used to carefully pass through the occluded segment. Angiography with the microcatheter should confirm that the guidewire is in the true lumen. The exchange micro guidewire is then sent into the micro catheter, and the microcatheter is exchanged out. The balloon catheter is advanced smoothly into the occluded segment along the exchange micro guidewire. After the occluded segment is dilated with the balloon, angiography with a guiding catheter is performed. Stents are deployed in cases of residual severe stenosis, vascular dissection and failure to maintain forward flow (according to the judgment of the neuroradiologist to select the stent). If one stent cannot completely cover the lesion, multiple stents can be implanted. Successful recanalization was defined as achieving a modified Thrombolysis in Cerebral Infarction (mTICI)³² grade of 2b or higher, coupled with residual arterial stenosis less than 50% in immediate post-procedural DSA imaging..

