To investigate whether endovascular recanalisation plus medical treatment is superior to medical treatment alone for symptomatic non-acute intracranial artery occlusion (sNA-IAO) in the primary outcome (any stroke or death within 30 days after enrollment or ischemic stroke in the territory of the qualifying artery from 30 days to 1 year after enrollment).

3. Statistical Hypotheses

The primary hypothesis is:

Patients in the endovascular recanalisation group are expected to demonstrate a lower incidence of primary outcome (any stroke or death within 30 days after enrollment or ischemic stroke in the territory of the qualifying artery from 30 days to 1 year after enrollment).

4. Study Design

The Endovascular Recanalization for Non-Acute Intracranial Artery Occlusion (ERNA-IAO) study is a multicenter, prospective, cohort study, this cohort prospectively enrolls consecutive patients with radiologically confirmed sNA-IAO at 6 comprehensive stroke centers in China from January 1, 2020 to October 31, 2023. All study centers were required to have performed at least 120 endovascular procedures annually, including at least 40 cases of endovascular interventions involving intracranial arteries. The interventional neuroradiologists at these centers had each performed over 100 endovascular procedures. All participants or their legal representatives provide written informed consent prior to enrollment. The technical feasibility of endovascular recanalization for all sNA-IAO patients in this study will be collaboratively evaluated by two experienced interventional neuroradiologists. The decision to select either medical treatment alone or additional endovascular recanalization is made by the patients themselves or their legal representatives. Patients are subsequently divided into two groups according to the treatment they received: the medical group and the endovascular recanalization group. The study protocol was approved by the Institutional Ethics Committee of Beijing Tiantan Hospital, (approval number: KY2020-114-02), and each subcenter, and will follow the STROBE (Strengthening the Reporting of Observational Studies in Epidemiology) guideline.

Endovascular recanalization (ER):

Patients will receive ER (details in procedure part in Supplement 1) plus medical treatment (same as the control group). All procedures are performed under general anesthesia by an experienced interventional neuroradiologist.

Medical treatment:

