5.1. Primary Outcome

The primary outcome is a composite of any stroke or death within 30 days after enrollment or ischemic stroke in the territory of the qualifying artery from 30 days to 1 year after enrollment.

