7.1 General Considerations for Data Analyses

All analyses will be performed with using SAS Version 9.4. All analysis output will use the following treatment group naming conventions and treatment order:

ER group: patients will receive ER (details in procedure part) plus medical treatment (same as the control group);

Medical group: patients will receive the medical treatment alone.

All statistics is two sided with a $P < 0.05$ considered significant.

Examination of Subgroups

The rates of the primary outcome will be presented for each level of the covariates listed below. We will assess the extent to which the treatment effect varies across levels of each subgroup using interaction tests.

Multiple Comparisons and Multiplicity

A single primary efficacy variable has been defined for this study, with all other efficacy variables identified as secondary or other. Similarly, only one treatment comparison is of interest in the study and therefore there are no requirements to adjust for multiple comparisons or multiple endpoints within this study.

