7.2 Data Handling Conventions

Premature withdrawal and missing data

If any subject withdraws prematurely from the study (prior to the final visit), they are required to complete the withdrawal visit in the case report form (CRF). The reasons for withdrawal will be presented in a summary table. For the purposes of summaries and analysis of clinic visit data, this visit will be assigned to the next scheduled clinic visit for that subject, regardless of whether the date falls within the next visit window.

Efforts will be undertaken at study sites to reduce the amount of missing data. For the primary efficacy outcome, multiple imputations in a model including strong prognostic variables will be used. Also, sensitivity analyses will be undertaken to explore the effect of missing data on the endpoint and test the robustness of the estimate. Ultimately, only patients who entirely completed the 1-year follow-up are included in the final analysis.

Event rates

The number of people and person-time of events should be recorded in detail and showing the event rate of each treatment group in summary statement.

The event rate for each treatment group will be calculated as: the sum of number of event for all the patients/the sum of number of treatment periods for all the patients.

Time to event analysis

Differences between treatments in the risk of any stroke (ischemic or haemorrhagic) event or composite vascular events during follow-up will be assessed using standard Kaplan-Meier time-to-event approaches. The time to the first event will be used in the model when there are multiple events of the same type. Patients will be considered censored at the time of study termination or death if there are no events occurred during the study.

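### Patients are grouped by treatment received but followed from enrollment, so a stroke or death that cancels a chosen ER falls outside the ER group; the synopsis gives a different rule.

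*SAP*

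**What the plan says.** The grouping rule appears in three places, in two forms.

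- SAP 4 (Study Design): "Patients are subsequently divided into two groups according to the treatment they received: the medical group and the endovascular recanalization group".
- Protocol 3.6: "Patients are subsequently divided into two groups according to the treatment they received: the medical group and the endovascular recanalization (ER) group".
- Protocol Synopsis, Treatments and Study Groups: "Patients are subsequently divided into two groups based on selection of treatment approach: the medical group and the ER group".

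SAP 7.1 adds a naming convention, "ER group: patients will receive ER (details in procedure part) plus medical treatment", which describes what the group is meant to get and does not choose between the two rules.

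The outcome clock starts at enrollment. SAP 5.1 begins: "The primary outcome is a composite of any stroke or death within 30 days after enrollment". Protocol 3.9.1 does the same.

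The procedure is a separate, later point. Table 1 gives ER its own columns after Screening and Baseline. Protocol 3.6.1 speaks of patients booked for it in advance: "All patients who are scheduled to undergo ER should receive dual antiplatelet therapy", with a lead-in of at least three days. No latest date for the procedure is set. Neither document says where to count a patient who chose ER and had a stroke or died before it.

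The primary comparison (SAP 7.5, Primary Efficacy Outcome) uses Kaplan-Meier curves, the log-rank test and Cox models. SAP 7.6 (Propensity Score Matching Analysis) repeats the same methods in a matched cohort. None of these uses the date of ER.

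**The concern.** In a non-randomised comparison the grouping rule is the definition of exposure. If that rule looks at what happened after time zero, group membership depends in part on the outcome: to enter the ER group, a patient must get from enrollment to the procedure without an event that cancels it. Such events are strokes and deaths soon after enrollment, which are the events that the 30-day part of the primary outcome is built to capture.

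Under the SAP rule, the patient whose ER is cancelled by an event has received only medical treatment, and so moves with the event into the medical group. The ER group loses an event and the medical group gains one. This runs in the direction of the SAP's own hypothesis of a lower incidence with ER. Covariate adjustment and propensity matching work on baseline variables and cannot put the event back.

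**Working it through.** **Which patients are affected**

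| Patient | By selection (synopsis) | By receipt (Protocol 3.6, SAP 4) |
|---|---|---|
| Chose ER, had ER, no earlier event | ER | ER |
| Chose ER, ER attempted but failed | ER | ER (success rate is itself a periprocedural outcome) |
| Chose ER, event first, ER still done | ER, event counted | ER, event counted |
| Chose ER, event first, ER cancelled | ER, event counted | Medical, event counted there |
| Chose medical, ER later | Medical | Not stated; listing unplanned ER as an outcome implies medical |

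The bias comes from the fourth row.

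**Size**

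The documents give no event rate, group size or interval from enrollment to procedure, so there is no figure of the plan's to reproduce. Every input below is an assumption: no true effect, one-year risk P = 0.12, equal numbers choosing each option, a wait of W days, and a share c of waiting-period events that cancel ER.

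- Risk of an event during the wait, even hazard: q = 1 − (1 − P)^(W/365). For W = 7, q = 0.00245.
- The same, front-loaded with a 5% 30-day risk: q = 1 − 0.95^(W/30). For W = 7, q = 0.01190.
- With k = c·q, apparent ER risk = (P − k)/(1 − k) and apparent medical risk = (P + k)/(1 + k).

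For W = 7 and c = 1:

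- Even: ER 0.11755/0.99755 = 0.11784; medical 0.12245/1.00245 = 0.12215; RR = 0.965.
- Front-loaded: ER 0.10810/0.98810 = 0.10940; medical 0.13190/1.01190 = 0.13035; RR = 0.839.

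Apparent RR when the true RR is 1:

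| Wait | Share cancelling | Even hazard | Front-loaded |
|---|---|---|---|
| 0 days | any | 1.00 | 1.00 |
| 3 days | all | 0.985 | 0.93 |
| 7 days | half | 0.982 | 0.92 |
| 7 days | all | 0.965 | 0.84 |
| 14 days | all | 0.931 | 0.70 |

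Group size also matters. If a share p chooses ER, the medical risk becomes ((1 − p)P + pk)/((1 − p) + pk). At 7 days with all cancelling, p = 30% gives 0.975 (even) or 0.879 (front-loaded), and p = 70% gives 0.943 or 0.761.

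**Check by simulation**

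Cox models were fitted to 200,000 simulated patients per scenario under a true hazard ratio of 1, with other assumed rates (30-day risk 3%, 5% or 10%; later risk 5% or 10%; waits of 3, 7 or 14 days). Grouping by selection returned 0.99 to 1.02 in all nine scenarios. Moving the events returned 0.90 to 0.94 at 3 days, 0.78 to 0.86 at 7 days and 0.60 to 0.72 at 14 days.

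**The case against.** The strongest reply is that the conflict is narrow and the bias hypothetical. Protocol 3.6 and SAP 4 agree, and only the synopsis differs. An analyst works from the SAP, and for most patients selection and receipt coincide. The bias needs a real gap, an event within it, and that event cancelling ER. Table 1 places the ER columns between baseline and discharge, which suggests one admission and a short gap. The three-day lead-in may precede enrollment. Protocol 3.6.1 counts one 90-day medication period from the procedure and 3.6.2 counts one from enrollment; this shows two reference dates, not that they lie far apart.

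Most of this stands and limits the severity. It does not remove the point, because the rule on which the two operative texts agree is the one that carries the bias.

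Two stronger readings are tempting.

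- A reader might infer that pre-ER events are deleted, because Table 1 repeats the eligibility mark in a pre-procedure column that exists only for ER. That is one mark in a table. No text removes a patient who fails the check, and SAP 7.3 counts completion and withdrawal over all enrolled participants.
- A reader might infer the same from SAP 7.2: "Ultimately, only patients who entirely completed the 1-year follow-up are included in the final analysis". Read literally, that sentence would exclude deaths in both groups. It is a separate problem and not specific to patients waiting for ER.

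**Conclusion.** The point holds as a should-fix. The grouping rule is stated in two ways. The version in the SAP, combined with follow-up from enrollment, assigns a cancelled ER and the event that cancelled it to the medical group. The direction of that shift is certain, always towards ER; its size is not.

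The plan does not show that the bias is large. The figures from 0.985 down to 0.70 rest wholly on assumed risks, waits and cancellation shares. The lowest needs a 14-day wait, a front-loaded hazard and every event cancelling ER, and a wait that long sits poorly with the Table 1 column order. If ER follows enrollment at once, the bias is nil.

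**What to change.** Reconcile the synopsis, Protocol 3.6, SAP 4 and SAP 7.1 to one rule, for example:

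> Patients are analysed in the group of the treatment strategy documented at or before enrollment, and all events from enrollment count in that group. Patients whose ER is cancelled or fails stay in the ER group. Patients in the medical group who later have ER stay there and are counted as unplanned revascularization. Failing the pre-procedure check does not remove a patient from the analysis.

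Neither document dates the treatment choice, and the data lists in Protocol 3.10.1 and 3.10.2 contain no field for it. Before any analysis, confirm that the choice and its date can be taken from consent or clinical records.

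- If they can, use the rule above for the primary analysis, and add a Cox model by treatment received, with ER as a time-dependent covariate, as a sensitivity analysis.
- If they cannot, make that time-dependent model primary, and fix this in writing before outcomes are seen. Protocol 3.10.2 already lists procedure times.

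Report the enrollment-to-procedure interval, and show cancelled procedures by reason in the flow chart that SAP 7.3 already plans.

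The cost is a few sentences, one flow-chart item, one model and a records check. Clinical care does not change. There are two downsides.

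- A choice reconstructed from records may be misclassified.
- The estimate is slightly diluted, because events before ER occur at the medical rate. With an assumed true post-procedure RR of 0.70 and a 7-day wait, the as-selected RR is [q + (P − q) × 0.70]/P: 0.08473/0.12 = 0.706 (even) or 0.08757/0.12 = 0.730 (front-loaded). If a further 5% never have ER for unrelated reasons, the factor 0.70 becomes 0.95 × 0.70 + 0.05 = 0.715, and the RR is 0.721 or 0.743.

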5.1. Primary Outcome

The primary outcome is a composite of any stroke or death within 30 days after enrollment or ischemic stroke in the territory of the qualifying artery from 30 days to 1 year after enrollment.

5.2. Secondary Outcomes

The secondary outcomes are as follows:

- (1) Mortality within 1 year;
- (2) Ischemic stroke outside the territory of the qualifying artery within 1 year;
- (3) Disabling stroke within 1 year;
- (4) Transient ischemic attack (TIA) in the territory of the qualifying artery within 1 year;
- (5) Unplanned revascularization (extracranial-intracranial [EC-IC] bypass surgery or ER) of the qualifying artery within 1 year;
- (6) Myocardial infarction within 1 year;
- (7) Composite vascular events within 1 year, including any stroke, myocardial infarction, and unplanned revascularization;
- (8) Quality of life assessment (EuroQol-Five-Dimensions [EQ-5D] scale questionnaire) at 1 year;
- (9) Modified Rankin Scale (mRS) score at 1 year;
- (10) Periprocedural outcomes, including the successful recanalization rate, periprocedural complications, residual stenosis, National Institute of Health Stroke Scale (NIHSS) score at 24-72 hours, death within 7 days, etc;
- (11) Restenosis or reocclusion (symptomatic or asymptomatic).

5.3 Safety Outcomes

An adverse event (AE) is defined as any unfavorable and unintended sign, symptom, or disease that occurs to a study subject during the use of a medical treatment or intervention, regardless of whether it is deemed related to the treatment. A preexisting condition should not be reported as an adverse event unless the condition worsens or episodes increase in frequency during the adverse event reporting period. A serious adverse event (SAE) is defined as any adverse event that results in death, is life-threatening, requires hospitalization or prolongation of existing hospitalization, results in persistent or significant disability or incapacity, causes a congenital anomaly

or birth defect, or requires medical intervention to prevent one of the above-mentioned outcomes. In this study, SAEs primarily refer to disabling strokes, symptomatic intracranial hemorrhages or death within 1 year after enrollment.

(Details of relevant definitions of outcome measures in Supplement 1)

6. Treatment Comparisons

The treatment comparison of interest in this study is to assess the effect of ER combined with medical treatment versus medical treatment alone in decreasing the risk of the primary outcome (any stroke or death within 30 days after enrollment or ischemic stroke in the territory of the qualifying artery from 30 days to 1 year after enrollment) in patients with sNA-IAO.

7. Statistical Analysis Method and Plan

